1. SYNOPSIS

A linkage of in-hospital data with data captured by basic IT systems used for home monitoring of patients with COPD (i.e. tablet computers and monitoring devices). EDGE2 builds upon EDGE¹ and will comprise:

- An exploration of using a tablet computer (the EDGE system) in clinical pathways in patients presenting with a COPD exacerbation/pulmonary infection in the hospital-to-home setting
- The integration of data collected whilst in-hospital (as part of usual care) with data captured via a tablet computer
- Obtaining data to inform the development of predictive algorithms which may provide early responses to changes in clinical condition and potentially avoid hospital admissions.

Study Title	A cohort study of a multi-component di	gital health intervention to improve			
	outcomes for people with chronic obstructive pulmonary disease				
Short title	EDGE2				
Study Design	Prospective cohort study with long-term mortality/hospital follow-up (5 years)				
Study Participants	Cohort 1: Patients aged ≥40 years with a clinical diagnosis of COPD				
	Cohort 2: Health professionals involved in delivering respiratory care				
Planned Sample Size	Cohort 1: Up to 200 patients (minimum	100), up to 30 of whom will also			
	take part in three interviews				
	Cohort 2: Up to 15 health professionals will take part in an interview				
	*please see appendix F for details of socially distanced procedures				
Planned Study Period	May 2019-2027				
	Objectives	Outcome Measures			
Primary	To determine the feasibility of	Obtaining 80-90% of patients in			
	integrating hospital data with ad-hoc	whom data can be obtained and			
	data collected at home.	matched from the in-hospital			
	system and the EDGE system.				
		Obtaining 80-90% of patients			
		where there is sufficient data from			
		the different sources to provide			

		clinically relevant data for use
		across the care pathway.
Secondary	1. To determine the impact of the	Outcome measures include:
	intervention.	SGRQ-C (respiratory
		questionnaire for COPD)
	2. To link patient data obtained in-	• EQ-5D (quality of life)
	hospital and within the community (at	MGL scale (medication
	home) to inform monitoring and the	adherence)
	development of predictive algorithms.	Smoking status
		Number of hospital admissions
	3. To validate/test physical function	Number of ICU admissions
	performance with monitoring data	Number of contacts with
	and assess feasibility of completing	health professionals (GP,
	the physical function assessment in	respiratory nurse)
	hospital.	Use of prescribed and over-
		the-counter medications, using
		self-report data, prescribing
		data and (in a sample)
		medication monitoring devices
		Physical function (sit-to-stand
		test)
		Costs of the digital
		intervention
		Patient death
		Patient hospital episodes
		Process measures:
		COPD care bundle (including but
		not restricted to: identify patient
		access to rescue packs, attendance
		at smoking cessation sessions and
		access to a self-management plan)

4. To determine the acceptability of the EDGE system.	Qualitative interviews
5. To determine the feasibility of implementing the EDGE system within existing health care practices and systems.	

2. ABBREVIATIONS

BRC	Biomedical Research Centre
CI	Chief Investigator
CRF	Case Report Form
CRT	Community Respiratory Team
CTRG	Clinical Trials & Research Governance
GCP	Good Clinical Practice
GP	General Practitioner
НСР	Health Care Professionals
HRA	Health Research Authority
ICF	Informed Consent Form
NHS	National Health Service
NIHR	National Institute for Health Research
PI	Principal Investigator
PIL	Participant/Patient Information Leaflet
R&D	NHS Trust R&D Department
REC	Research Ethics Committee

SD	Socially distanced
SOP	Standard Operating Procedure

3. BACKGROUND AND RATIONALE

New technologies bringing together novel approaches to monitoring, internet-based communication and predictive algorithms offer the potential for major advances in health care delivery. Digital health care, also termed telehealth or m-health, recognizes the potential for addressing problems associated with increasing numbers of people with long-term conditions, a requirement to support people in their own homes, and provide a much greater focus around self-management. New technologies can focus attention on delivery of care at a wider scale and lower cost.

Central to efforts to deliver digital health solutions are systems that obtain and make available data already captured during NHS care. Such systems can inform predictive algorithms to personalize help and advice, and where appropriate, provide alerts to patients and clinicians. Alerts could identify cases where additional assessment is perhaps needed or where treatment could be escalated to help the patient. Better monitoring, by bringing together clinical data from hospital admissions, accessing electronic health record data and capturing home-monitoring data is an ambitious, but deliverable means to identify individuals at risk of condition deterioration.

Building on the NIHR funded SEND project that has created a secondary care environment allowing capture of clinical measurements across the organisation², and the EDGE programme that captures data in a home setting^{1,3}, the NIHR Oxford BRC EDGE2 programme will focus on a cohort of individuals with chronic obstructive pulmonary disease (COPD) following hospital attendance/admission for an exacerbation or pulmonary infection with the aim of improving management of COPD across the hospital-to-community interface. Future potential applications of this system are to reduce readmissions and encourage early treatment of patient deterioration.

Hospital episodes of COPD are well characterized with over 4,000 COPD emergency admissions (many for exacerbations) in the Oxford University Hospitals between January 2013 and April 2017. Of patients admitted, approximately 1 in 4 are re-admitted within 3 months; highlighting that efforts to target the prevention of hospital re-admissions are warranted. Prior to the EDGE project¹, daily community data was not available over longer periods of time. Therefore, bringing the in-hospital and the community data-sets together in this study (EDGE2) will guide assessment of an individual's "usual state" based on prior-data at the point of hospital attendance/admission, during their hospital stay as well as following hospital discharge to inform personalized models to guide care.^{4,5} In addition, new monitoring devices will be used with the intention of informing future studies developing enhanced algorithms. The

frequency and specific method with which data will be captured will be counterbalanced to minimise patient intrusion whilst simultaneously maximise measurement precision.

EDGE2 will explore the feasibility of linking data collected during hospital attendance/admission and from the community. To build on EDGE findings, additional monitoring devices will be incorporated into the EDGE platform and qualitative insights will help inform the development of an advanced EDGE platform for future use. How the additional data collected may improve established clinical pathways for COPD management will be considered. The findings of this study will inform subsequent studies looking at producing predictive algorithms to support clinicians (physician-led) and establish the best (most efficient) modes of monitoring clinical state in the COPD population.

Data collection will take the form of in-hospital data, tablet data, monitoring data as well as qualitative investigations (both patients and health professionals involved in delivering respiratory care to capture qualitative insight into tablet use and integration within clinical care). Key deliverables include proof-of-concept for data collection across the in-hospital to community continuum, establish acceptability and feasibility for an extended EDGE system and ultimately capture data that will inform future clinical trials and roll-out of these approaches within digital health care.

4. SOCIALLY DISTANCED STUDY PROCEDURES (2020 PROTOCOL ADDITION)

Due to the COVID-19 global health pandemic there is an on-going need to ensure that research activities can continue with little to no face-to-face contact. People with COPD are a vulnerable cohort that continue to require frequent discussions with and assessment from members of the community respiratory team (CRT). At a time when many patients do not feel comfortable seeing their care-team face-to-face, EDGE2 presents a unique opportunity for the Oxford Respiratory health team to be able to remotely monitor their patients in addition to allowing the study objectives to be delivered. The EDGE system was developed with eventual deployment into a care pathway in mind, but the current research protocol designed pre-COVID includes a number of procedures that, whilst addressing secondary aims, render the study as currently designed impossible to deliver at a time when social distancing and rigorous infection control must be maintained. The procedures presented in Appendix F: Socially Distanced Study Procedures, serve to adapt the study design to avoid face-to-face contact whilst also making the system practical for use by the CRT to monitor their patients. These adaptations, including the increased duration of follow up, will allow the research to recommence safely and collect study data whilst also supporting the delivery of patient care.

Where relevant procedural changes may be in effect thus resulting in a change to the protocol outlined below, these areas will be marked with a reference to the applicable section of Appendix F.

Objectives	Outcome Measures	Time points of the outcome measures		
Primary	Obtaining 80-90% of patients in whom	Initiation of data linkage		
To determine the feasibility of	data can be obtained and matched	will take place upon		
integrating hospital data with ad-hoc data collected at home	from the in-hospital system and the EDGE-2 platform. Obtaining 80-90% of patients where there is sufficient data to provide clinically relevant data for use across	provision of consent. In-hospital data will be retrieved from point of hospital attendance/admission to		
	the care pathway.	the point of hospital discharge.		
Secondary1. To determine the impact of the intervention.2. To link patient data obtained	 SGRQ-C (respiratory questionnaire for COPD) EQ-5D (quality of life) MGL scale (medication adherence) 	These outcome measures will be captured at baseline and ~52 weeks; apart from:		
in-hospital and within the community (at home) to inform monitoring and the development of predictive algorithms.	 Smoking status Number of hospital admissions Number of ICU admissions Number of contacts with health professionals (GP, respiratory nurse) 	Physical function assessment ¹ : This will be completed at baseline (either during hospital admission (if feasible) or at recruitment home		
3. To validate/test physical function performance with monitoring data and assess feasibility of completing the physical function assessment in hospital.	 Use of medications, prescribed and un-prescribed via self-report, prescribing data and (in a sample) medication monitoring devices Physical function (sit-to-stand test) Costs of the digital intervention 	visit, within ~6 weeks of discharge), plus within ~4 weeks (if recruited in hospital), ~12 weeks, ~24 weeks, and ~52 weeks from the date of consent.		

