6. STUDY DESIGN

EDGE2 is a 12-month cohort study and has an overarching aim to establish a model for a clinical system that can be integrated into current patterns of clinical care. The data collection procedures will capture valuable data to inform future studies that aim to identify (support a response to) early changes in clinical condition e.g. possible patient deterioration. Looking ahead, this could help de-risk selfmanagement by patients accessing monitoring tools at home to gain a greater awareness of their condition (which may reduce the chance of hospital re-admission). EDGE2 will explore proof-of-principle for combining hospital and community data. A flow chart for the study design is provided in Appendix A.

Up to 200 patients diagnosed with COPD will be recruited after presenting with a COPD exacerbation or pulmonary infection.

Baseline assessment:

Briefly, patients will be asked to complete several questionnaires as well as complete a physical function assessment³ (sit-to-stand test, if the participant is physically capable), either whilst they are still in hospital or after discharge by a member of the clinical research team. Further details are provided in **Section 8.4** and enclosed with this application is a copy of the baseline questionnaire.

In-hospital data:

In-hospital data will come from the databases of the Oxford University Hospitals Clinical Information Systems, which are used for routine patient care and clinical governance (see Appendix B). Hospital data will only be obtained for patients taking part in EDGE2 who will have provided consent for the researchers to access this data.

Intervention:

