7.2. INCLUSION CRITERIA

7.2.1. COHORT 1 (PATIENTS)

- Patient is willing and able to give informed consent
- Aged 40 years or older
- A clinical diagnosis of chronic obstructive pulmonary disease recorded in their medical history
- Current or ex-smoker
- Acute hospital attendance/admission for an exacerbation of chronic obstructive pulmonary disease or pulmonary infection in the last 3 months
- Able to complete questionnaires (electronic or paper) and use the tablet computer
- Post-discharge destination not a medical facility or prison
- Lives in Oxfordshire or surrounding counties
- Able to adequately understand verbal and written English.

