8.5. INTERVENTION

Patients who consent to take part in the study will be provided with a tablet computer during their hospital stay or at a home visit after discharge (depending on when consent to take part is obtained). The tablet computer will run the EDGE mHealth application¹. Patients will also be provided with monitoring devices (e.g. Nokia/Withings Go and Nonin) to capture oxygen saturation, heart rate and physical activity (movement). Minor changes will be made to the existing EDGE system so that it communicates with the monitors and offers up-to-date information to patients. The monitoring devices will be commercially available, CE marked and will be used in accordance with intended usage as specified by the manufacturers. They will collect data and transfer this to the tablet via Bluetooth at regular intervals (e.g. daily). A member of the research team will telephone participants in the event any technical or well-being concerns are raised, whilst monitoring the incoming data. These telephone calls will likely be sporadic and brief. For instance, if data transfer does not happen as intended or the data that is transfer or encourage wear (as appropriate). If any technical concerns cannot be resolved over the telephone, additional visits may be made to participants to attempt to resolve the issue inperson.

Patients will be shown how to use the tablet computer and monitors upon entry into the study, either in hospital or after discharge. They will also be provided with a manual providing brief, clear and concise instructions about the mHealth application and tablet computer (see enclosed patient monitor manual). This manual will also include contact details for the clinical research team in the event technical or other relevant queries arise.

Patients will use the tablet computer to provide details about their clinical condition (i.e. COPD symptoms) as soon as they would like to once they have received the system. Patients will also be encouraged to wear a wrist-worn physical activity monitor to collect a profile of their physical activity. To monitor oxygen saturation and heart rate, patients will be asked to wear the pulse oximeter every day for a brief period after completing the COPD symptom diary on the tablet computer. Instructions on how to wear the pulse oximeter will be available to patients on the tablet computer.

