24. APPENDIX E: MEASUREMENTS MATRIX

	At baseline (either in hospital or within ~6- weeks of discharge)	At 4 weeks	At 12 weeks	At 24 weeks	At 52 weeks	Data accessed from hospital records	An ongoing measure (up until 5 year follow up)
PRIMA	RY OUTCOME	MEASURE	S				•
Linkage of hospital and tablet data	x						x
SECON	IDARY OUTCOM	ME MEASU	JRES		-		•
SGRQ-C	х				x		
EQ-5D-5L	х				x		
MGL scale	х				x		
Smoking status	х				х		
Self-efficacy	х				x		
Admissions to hospital	x [in preceding year]				x [any subsequent visits]	x	
Admissions to ICU	x [in preceding year]				x [any subsequent visits]	x	
Number of contacts with healthcare professionals	x [in preceding year]				x [any subsequent visits]		
Medication and oxygen therapy	x				x		
Physical function	x	х	х	х	x		
Costs of the digital intervention	x				x		
Death		х	х	х	х		х
COVID-19 Status	x	х	х	х	x		
Hospital episode statistics							х
SECON	IDARY PROCES		ES				
COPD care bundle	х	х					

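### Secondary objective 1 claims to measure the intervention's impact, but this single-arm design can only describe change, and its admission count can fall with no effect

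*Protocol*

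**What the plan says.** The Synopsis and the objectives table (Section 5) give secondary objective 1 as "To determine the impact of the intervention". The design is a "Prospective cohort study with long-term mortality/hospital follow-up (5 years" years). Section 8.5 gives the system to everyone: "Patients who consent to take part in the study will be provided with a tablet computer". No concurrent, matched or historical comparator appears anywhere.

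The outcomes listed against the secondary objectives include SGRQ-C, EQ-5D and the number of hospital admissions, captured at baseline and about 52 weeks. In Appendix E, the baseline entry for hospital admissions is "x [in preceding year"], and the 52-week entry covers any later visits. Nothing there removes the episode that made the patient eligible.

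That episode is an inclusion criterion (Section 7.2.1): "Acute hospital attendance/admission for an exacerbation of chronic obstructive pulmonary disease or pulmonary infection in the last 3 months". Baseline is taken in hospital or within about 6 weeks of discharge (Section 8.4). Under the socially distanced route, it is taken within 2 weeks of consent, in patients who attended or were discharged within the last 90 days (Sections 25.1 and 25.3.1).

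On re-admission, Section 3 says that of patients admitted, "approximately 1 in 4 are re-admitted within 3 months".

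**The concern.** The word impact is causal. With one arm, the only contrast that can speak to it is each patient against their own past, and two features of the protocol tilt that contrast towards apparent benefit.

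- **Admissions.** Patients enter because of a recent acute episode. If it was an admission and is counted, the preceding year holds one event that the entry rule guarantees. The follow-up year has no such guaranteed event.
- **Questionnaires.** SGRQ-C and EQ-5D baselines taken during or soon after an exacerbation can improve as the patient recovers, with or without a tablet.

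The study is meant to inform later trials and roll-out (Section 3). A fall in admissions reported under the heading of impact could be carried into those decisions as evidence of benefit.

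**Working it through.** The protocol gives no effect size, power or sample-size figure for this objective, so there is none to reproduce. The check asks what the Appendix E windows would show if the system had no effect.

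**Inputs**
- Re-admission: 1 in 4 within 3 months (Section 3).
- Preceding window: one year, qualifying episode not excluded (Appendix E).
- Follow-up window: about one year (Section 6).
- Assumptions: admissions follow a Poisson process at constant annual rate L; follow-up is complete; a share q of qualifying events were attendances without admission. The protocol does not give q, so it is varied.

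**Rate.** L = −ln(1 − 0.25) / 0.25 = 1.15 per year.

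**Recruited at the qualifying episode.** Preceding-year mean = (1 − q) + L. Follow-up mean = L. No-effect fall = (1 − q) / [(1 − q) + L].
- q = 0: 2.15 before, 1.15 after; fall = 1 / 2.151 = 46%.
- q = 0.5: 1.65 before, 1.15 after; fall = 0.5 / 1.651 = 30%.
- q = 1: no built-in fall in admissions.

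**Selected on at least one admission in the last 90 days.** Preceding-year mean = 0.75L + 0.25L / (1 − e^(−0.25L)) = 0.863 + 0.288 / 0.25 = 2.01. Follow-up mean = 1.15. Fall = 43%.

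**Sensitivity to the rate, q = 0**

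| L per year | Fall, recruited at episode | Fall, 90-day selection |
|---|---|---|
| 0.5 | 67% | 65% |
| 0.8 | 56% | 53% |
| 1.15 | 46% | 43% |
| 1.5 | 40% | 36% |

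**Qualifying episode left out, constant rate.** Both windows have mean L, so the built-in difference is zero.

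**Qualifying episode left out, risk higher just after discharge.** Keep the first 3 months at the 1-in-4 level (0.288 expected admissions), and let the rate be r for the other 9 months and for the preceding year. Follow-up mean = 0.288 + 0.75r; preceding mean = r.
- r = 0.4: 0.588 against 0.4, a rise of 47%.
- r = 0.8: 0.888 against 0.8, a rise of 11%.

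The exclusion removes one bias, but the comparison still does not estimate an effect.

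**The case against.** **No test of counts is written down.** This is correct. Section 12.1.1 names repeated-measures analysis of (co)variance and linear regression for continuous variables, and gives no method for counts. Appendix E is a collection schedule, and the analysis plan is not shown. A reader might infer that the study is almost certain to declare a significant reduction. In simulation under no effect, a two-sided 5% paired t-test does show a significant fall in 100% of studies at 100 or 200 patients if every qualifying event was an admission, and in about 87% and 99% if half were. That test is only an illustration, and the protocol does not specify it. What stands is that the objective's wording, the single arm, the entry rule and the windows are fixed here, and an analysis plan cannot supply a comparator.

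**The qualifying episode may not be counted.** This is partly right. Section 8.4 asks about previous admissions and past attendances, so for a patient consented during the stay the current episode could fall outside. For patients consented after discharge, including the socially distanced route, the episode is over and lies inside the preceding year.

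**The excess is not general.** This is also right. A reader might extend it to ICU admissions and GP or nurse contacts, but entry requires neither, so the one-event excess does not carry over. For admissions it shrinks as attendance-only entries increase.

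**The rate is extrapolated.** The 1-in-4 figure covers the first 3 months after admission, and the cohort excludes some high-risk patients (Section 7.3.1). A lower long-run rate makes the relative fall larger.

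**Ascertainment is already covered.** A reader might infer that admissions are badly captured, because in-hospital data come from one trust while patients may live in surrounding counties. The documents do not support that for follow-up: national hospital episode data are a listed outcome to 5 years, and withdrawal options 1 and 2 (Section 9.1) keep them. The remaining gap is the preceding year, because Section 11.1 describes that extract as running forward from discharge.

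**Conclusion.** The concern holds and should be fixed. As written, objective 1 asks for something this design cannot deliver, and the preceding-year admission window is left open in a way that can create a fall from nothing.

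With every qualifying event an admission, that fall is about 36% to 67% over assumed rates of 0.5 to 1.5 per year. At the rate derived from the protocol's own figure it is 46%, or 43% under 90-day selection, and about 30% if half the events were attendances only. These sizes rest on a constant rate, complete follow-up and the qualifying episode being counted. Recovery in SGRQ-C and EQ-5D acts in the same direction, but the documents give nothing from which to size it.

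This is one secondary objective in a feasibility study. The data-linkage primary outcome is untouched, and no decision rule depends on objective 1.

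**What to change.** 1. Reword objective 1, in the Synopsis and Section 5, as describing change over 52 weeks. State that no effect will be attributed to the system.
2. For hospital admissions, define the preceding-year window as the 12 months ending the day before the qualifying attendance or admission, exclude that episode, and apply the same rule whether consent was given in hospital or later. Report follow-up as a rate per person-time to death or end of permission. State that this removes the built-in fall but does not measure effect, because higher risk soon after discharge could produce a spurious rise.
3. Optionally, where consent and the data-sharing agreement allow, take both windows from the same national hospital episode source. The request would then have to reach back to 12 months before the qualifying episode.

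Items 1 and 2 cost only protocol wording. Item 3 needs an earlier start date on the data request. The downside is that the objective reads less ambitiously and any apparent reduction in admissions will be smaller.
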